6.1.2 Unscheduled visits

Unscheduled visit measurements of laboratory data, vital signs, and ECG will be used for computation of baseline and worst values and/or grades. Re-windowing for unscheduled visits will not be performed.

6.1.3 Duplicated visits

Depending on the statistical analysis method, single values may be required for each analysis window. For example, change from baseline by visit usually requires a single value per visit. Unless otherwise noted throughout the rest of this document, when a single value is needed, the following rule(s) will be used:

- If more than 1 assessment occurs during the same nominal visit, select the record closest to the nominal day for that visit.
- If there are 2 assessments that are equidistant from the nominal day, the data of the assessment after the scheduled study day will be used.
- The last measurement will be used if multiple measurements are taken on the same day.

6 Reference List

John Crowley, Donna Pautler Ankerst. Handbook of Statistics in Clinical Oncology. *Chapman & Hall/CRC.* 2006.

Carter RH and Barrington RA. Signaling by the CD19/CD21 complex on B-cells. *Curr Dir Autoimmun.* 2004;7:4–32.

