7.4.4 Vital Signs

Planned time points for vital signs are provided in the SoE ([Table 2](#)). Vital signs include the measurements of arterial blood pressure (systolic and diastolic), heart rate, respiratory rate, and body temperature and will be performed according to the institutional standards.

For Day 1 of each cycle and C1D2, vital signs are to be measured before the start of the study drug infusion and at the end of infusion.

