4.9 Safety Analyses

All safety analyses will be based on the all-treated population.

General common rules

All safety analyses will be performed on the all-treated population, unless otherwise specified, using the following common rules:

- The baseline value is defined as the last non-missing value or measurement taken up to the first dose in the study.
- The analyses of the safety variables will be essentially descriptive and no systematic testing is planned.

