4.9.4 Vital Signs

Descriptive statistics (mean, standard deviation, median, and range) for vital signs data, including systolic and diastolic blood pressure, heart rate, respiration rate, and body temperature will be calculated for the raw data and for their changes from baseline at each scheduled assessment.

All vital signs data will be listed together with body weight.

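### The SAP names no time point for dosing-day vital signs, and its default same-day rule would put end-of-infusion values into the by-visit change from baseline

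*SAP*

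**What the plan says.** Protocol 7.4.4 asks for two sets of readings on Day 1 of each cycle and on C1D2: "vital signs are to be measured before the start of the study drug infusion and at the end of infusion". Those days cover every planned dosing day. Change in vital signs is one of the secondary safety endpoints (protocol Section 3, Table 3).

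SAP 4.9.4 gives descriptive statistics "for the raw data and for their changes from baseline at each scheduled assessment". It does not distinguish pre-infusion from end-of-infusion readings. It also states that all vital signs data will be listed.

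SAP 4.9 fixes the reference value: "The baseline value is defined as the last non-missing value or measurement taken up to the first dose in the study".

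SAP 6.1.3 covers several values at one visit. Its scope is set by "Unless otherwise noted throughout the rest of this document, when a single value is needed, the following rule(s) will be used", and its example is "For example, change from baseline by visit usually requires a single value per visit". The first rule is "If more than 1 assessment occurs during the same nominal visit, select the record closest to the nominal day for that visit". The second breaks ties between records equally far from the nominal day by taking the later one. The third is "The last measurement will be used if multiple measurements are taken on the same day". The SAP notes no exception for vital signs.

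**The concern.** The last-measurement rule suits unplanned repeats, where the later reading replaces a doubtful earlier one. The two dosing-day vital-sign sets are not repeats. They are planned readings taken in different conditions, one before drug and one after an infusion. Read literally, the rule keeps the second and leaves the first out of the by-visit summary, although protocol 7.4 makes pre-dose assessment the default for safety measurements on dosing days.

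What is at stake is how the vital-signs table can be read. A change across cycles in blood pressure, heart rate or temperature would be combined with whatever the infusion did that day. Visits with and without an infusion would be summarised as if they were comparable.

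**Working it through.** The plan states no figure to reproduce here. The check applies the SAP rules to the protocol schedule.

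**Inputs**
- Visits with vital signs (protocol Table 2): screening, C1D1, C1D2, C1D9, C2D1, C3D1, Day 1 of Cycles 4 to 6, and EoT.
- Two readings on each dosing day (protocol 7.4.4).
- Planned treatment of 4 to 6 cycles (protocol 4.1).
- Selection rules (SAP 6.1.3) and baseline definition (SAP 4.9).

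**Step 1: which record is kept.** The two dosing-day readings share a date, so they are equally close to the nominal day and on the same side of it. The first two rules cannot separate them. The third rule decides and keeps the end-of-infusion reading. A visit moved by a day within its window gives the same result.

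**Step 2: how many visits are affected.**

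| | 4 cycles | 6 cycles |
|---|---|---|
| Dosing days | C1D1, C1D2, C2D1, C3D1, C4D1 = 5 | those 5 plus C5D1, C6D1 = 7 |
| Other visits after first dose | C1D9, EoT = 2 | C1D9, EoT = 2 |
| Visits with a reading after first dose | 5 + 2 = 7 | 7 + 2 = 9 |
| Visits showing an end-of-infusion value | 5 of 7 (71%) | 7 of 9 (78%) |
| Pre-dose readings after baseline that are not summarised | 5 − 1 = 4 | 7 − 1 = 6 |

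The 1 subtracted in the last row is the C1D1 pre-dose reading, which precedes the first dose and can serve as baseline.

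**Step 3: what the table would contain.** Let B be baseline, PRE the pre-infusion reading and EOI the end-of-infusion reading at a dosing visit.

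- Dosing visits: EOI − B = (PRE − B) + (EOI − PRE). The first term is change since baseline; the second is change over that day's infusion. Only the sum would be tabulated.
- C1D1, when its pre-dose reading is the baseline: PRE = B, so the entry is the change over the first rituximab infusion alone.
- C1D9 and EoT: reading − B, with no same-day infusion.

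**Step 4: which infusion.** On C1D1 the infusion is rituximab and on C1D2 it is loncastuximab tesirine (protocol Table 4). From Cycle 2 both are given on Day 1, loncastuximab tesirine first, with at least 30 minutes between them (protocol 6.2.2); rituximab may then be subcutaneous (protocol 6.1.2). Protocol 7.4.4 does not say whose end of infusion is meant. Either reading is post-infusion, so the counts in Step 2 stand, but the second term in Step 3 does not have one constant meaning across visits.

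**The case against.** The strongest reply is that the rule is conditional. SAP 6.1.3 is headed as a rule for duplicated visits, operates only where one value is required, and says that by-visit change usually requires one. The two readings could be treated as two scheduled assessments, both summarised, and the last-measurement rule would never choose between them. This stands as a possible reading, which is why the point is worded conditionally. Against it, the SAP does not say so, Table 2 has a single vital-signs entry per visit day, and the SAP offers by-visit change from baseline as its own example of a single-value analysis.

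A reader might infer that the pre-dose data are discarded, that the acute infusion effect is never shown, or that the table answers no safety question. The documents do not support these readings. SAP 4.9.4 lists all vital signs. Protocol 9.8.3 plans worst-case summaries across scheduled and unscheduled visits, and SAP 6.1.2 refers to worst values for vital signs. The C1D1 entry itself would show the change over the first infusion. Infusion-related reactions are tabulated separately among the treatment-emergent adverse events (SAP 4.9.1.1). Nor can C1D9 and EoT values be called resting values: protocol 7.4.4 asks only for institutional standards, and the five-minute rest belongs to the ECG section (7.4.7).

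The scale of the consequence is also fairly challenged. SAP 4.9 makes the safety analyses essentially descriptive, without systematic testing, and the study was discontinued with 41 patients treated (SAP 3.2).

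**Conclusion.** The point holds as a minor one. The SAP leaves the dosing-day time point unstated, and the default it supplies, if used, gives a by-visit table in which 5 of 7 (or 7 of 9) entries per patient are post-infusion values against a pre-infusion baseline, with 4 (or 6) later pre-dose readings left out. That is a poorer summary of a named secondary safety endpoint than the scheduled data allow.

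The conclusion assumes that the default is applied to the by-visit change, that both readings are taken as scheduled, and that the patient completes the stated number of cycles. It reaches only the descriptive vital-signs tables. The listing, adverse-event tables and response analyses do not depend on it.

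**What to change.** In SAP 4.9.4, summarise vital signs by visit and time point:
- pre-infusion value and its change from baseline;
- end-of-infusion value and its change from the same day's pre-infusion value, stating which infusion's end is used from Cycle 2 on.

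In SAP 6.1.3, limit the last-measurement rule to repeats at the same nominal time point.

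The cost is SAP wording and one extra row or column per visit. Both readings are already scheduled, so no further assessments are needed. This assumes that the CRF records the time point in a form that can be analysed. The CRF is not among the documents, so that should be confirmed first.
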